### 5.0 **STUDY TREATMENT**

#### 5.1 The Ingestible Sensor System

The system consists of 1.0 mm x 1.0 mm x 0.45 mm ingestible sensor and an on-body wearable sensor. The ingestible sensors are activated by gastric fluids, independent of the acidity level, and communicate unique identifying signatures to the body surface. The system uses a conductive method of communication, not radio frequency, which ensures the information is confined to the body of the user and preserves privacy. The wearable sensor counts the number of times each unique signature is received. For pre-study, the ingestible sensors were attached to inert tablets and co-ingested with the TB medications. The system recorded the date and time of an ingestion event after a unique signature was received 10 times. The ingestible sensors are designed to communicate for approximately 7 minutes after which they are inactive and get eliminated in the feces. The system is capable of identifying and differentiating among multiple simultaneously ingested sensors.

#### 5.2 Regimens, Administration, and Duration

Study Treatment is defined as:

DHFS Group: over-encapsulated ingestion sensor plus a fixed-dose combination of isoniazid-rifampin (Rifamate) (study supplied) (alternatively in Phase 1, Rifamate with co-ingestion of an encapsulated edible sensor)

SOC Control Group: isoniazid plus rifampin, or Rifamate (by prescription)

### 5.2.1 Regimens

DHFS Group:

Rifamate (combination of isoniazid 150 mg and rifampin 300 mg) over-encapsulated with ingestion sensor - 2 capsules orally QD (provided by the study through the AVRC pharmacy)

SOC Control Group:

isoniazid 300 mg -1 tablet orally QD plus rifampin 300 mg - 2 capsules orally QD, or Rifamate (combination of isoniazid 150 mg and rifampin 300 mg) - 2 capsules orally QD (provided by the PHS, OCHCA, or study physician)

### 5.2.2 Administration

Isoniazid and rifampin, or Rifamate, will be administered orally as described above, preferably on an empty stomach (at least one hour prior to or two hours after a meal) first thing in the morning.

### 5.2.3 Duration

Subjects will receive study treatment for a minimum of 6 weeks up to a maximum of 12 months on study, depending on time left to complete treatment.

## 5.3 Study Treatment (DHFS IS-RM) Formulation and Preparation

### 5.3.1 Formulation

Isoniazid-rifampin (Rifamate) fixed dose formulation capsules over-encapsulated with ingestible PDH sensor. Store at 25C (77F), excursion permitted to 15-30^0C (59-86F) (see USP Controlled Room Temperature); protect from excessive heat and humidity.

### 5.3.2 Preparation

Ingestible PDH sensor and isoniazid-rifampin (Rifamate) will be over-encapsulated with Capsugel gelatin capsules, and dispensed by the AVRC pharmacy. The final study product will be packaged in white, high density polyethylene bottles. Each bottle will contain a sufficient quantity of study drug to last until the subject's next scheduled visit.

5.4 Study Product Supply, Distribution, and Accountability

5.4.1 Study Product Supply/Distribution

For the DHFS group, ingestion sensors will be purchased from Proteus Digital Health, Inc. and anti-TB drugs (Rifamate) and over-encapsulation will be provided by the AVRC pharmacy. The study product (IS-RM) will be supplied by the study.

For the control group receiving SOC, isoniazid and rifampin, or Rifamate, will not be supplied by the study, but will be made available to subjects via prescription at a public health pharmacy.

5.4.2 Study Product Accountability

The clinical site pharmacist is required to maintain complete records of all study products received, compounded (over-encapsulated), and subsequently dispensed for this study. All unused study products must be returned to the sponsors after the study is completed or terminated.

5.5 Concomitant Medications

5.5.1 Required Medications

WHILE PARTICIPANTS ARE TAKING ISONIAZID OR RIFAMATE (isoniazid in combination with rifampin), PYRIDOXINE (VITAMIN B6) 25 MG OR 50 MG MUST ALSO BE GIVEN ONCE DAILY.

5.5.2 Prohibited Medications:

- All investigational drugs.
- Any immunomodulators.
- Systemic cytotoxic chemotherapy.
- The following antiviral drugs: ritonavir, Stribild®, atazanavir, darunavir, fosamprevavir, saquinavir, tipranavir, delavirdine, etravirine, and rilpivirine.
- All herbal products should be avoided because of the unknown drug interactions between herbal products and TB drugs used in this study.

5.5.3 Precautionary Medications

5.5.3.1 Precautionary Medications with Rifampin

Medication Class	Precautionary Medications
ACE Inhibitors	Enalapril
Antiarrhythmics	Disopyramide Mexiletine

Medication Class	Precautionary Medications
	Quinidine Tocainide
Antibiotics	Chloramphenicol Clarithromycin Dapsone Doxycycline Fluoroquinolones
Anticoagulants	Warfarin
Anticonvulsants	Phenytoin
Antimalarials	Quinine Atovaquone
Antiretrovirals	Efavirenz Nevirapine Raltegravir Zidovudine Dolutegravir
Antipsychotics	Haloperidol
Azole Antifungals	Fluconazole Itraconazole Ketoconazole
Barbiturates	Phenobarbital
Benzodiazepines	Diazepam
Beta-Blockers	Propranolol
Calcium Channel Blockers	Diltiazem Nifedipine Verapamil
Cardiac Glycoside Preparations	Digoxin
Corticosteroids	Prednisone
Fibrates	Clofibrate
Hormonal Contraceptives/Progestins	Ethinyl estradiol Levonorgestrel
Oral hypoglycemic agents	Sulfonylureas
Immunosuppressants	Cyclosporine Tacrolimus
Methylxanthines	Theophylline
Narcotic analgesics	Methadone
Phosphodiesterase-5 (PDE-5) Inhibitors	Sildenafil
Thyroid preparations	Levothyroxine

Medication Class	Precautionary Medications
Tricyclic Antidepressants	Amitriptyline Nortriptyline

5.5.3.2 Precautionary Medications with Isoniazid:

- Carbamazepine
- Chlorzoxazone
- Disulfiram
- Ketoconazole
- Phenytoin

The physician responsible for prescribing TB medications to subjects should be made aware of the following: It may be necessary to adjust the dosages of some medications when given concurrently with isoniazid/rifampin. To avoid adverse drug interactions, package inserts of anti-TB agents and other concomitant medications should be referenced whenever a concomitant medication is initiated or dose changed, to avoid drug interaction AEs.

5.5.4 Food Interactions

Prescribing physicians should be aware that since isoniazid has some monoamine oxidase inhibiting activity, an interaction with tyramine-containing foods (cheese, red wine) may occur. Diamine oxidase may also be inhibited, causing exaggerated response (e.g., headache, sweating, palpitations, flushing, hypotension) to foods containing histamine (e.g., tuna, other tropical fish). Tyramine- and histamine-containing foods should be avoided.

## 6.0 CLINICAL AND LABORATORY EVALUATIONS

### 6.1 Schedule of Events

Table 1.

Evaluation	Screening	Phase 1				Randomization	Phase 2							Completion of Treatment/ End of Study or Premature Discontinuation
		Week 1 Day 0	Week 1 Visit 1	Week 2 Visit 2	Week 2 Visit 3		Day 0	Daily	Weekly	Wk 2	Wk 4	Wk 8	Wk 12 and every 4 weeks	
Visit Window		Within 45 days of Screening								+ 7 days	+ 7 days	+ 14 days	+ 14 days	
Informed Consent	X													
Demographics and Language	X													
Documentation of TB	X													
Medical History	X													
Medication History (last 30 days)	X													
Toxicity/AE Evaluation	X	X	X	X	X		X			X	X	X	X	X
Targeted Exam	X	X					X			X	X	X	X	X
Concomitant Meds (since last visit)		X	X	X	X		X			X	X	X	X	X
Initiation of study medication		X					X*							
Randomization						X								
PDH System														
Subject training		X	X				X*							
Observation with PDH Patch		X	X	X	X		X*			X*	X*	X*	X*	X*
Patch change (by subject)		X		X			X*		X*					
Witnessed Rifamate doses		X	X	X	X		X*							
Adherence Intervention Based on PDH Sensor**								X*						

Evaluation	Screening	Phase 1				Randomization	Phase 2							Completion of Treatment/ End of Study or Premature Discontinuation
		Week 1 Day 0	Week 1 Visit 1	Week 2 Visit 2	Week 2 Visit 3		Day 0	Daily	Weekly	Wk 2	Wk 4	Wk 8	Wk 12 and every 4 weeks	
Laboratory Evaluations														
Hematology§	X						X			X	X	X	X	X
Liver Function Tests§	X						X			X	X	X	X	X
Chemistry§	X						X			X	X	X	X	X
Pregnancy Testing (and whenever pregnancy is suspected)	X	X												
Stored Plasma/Serum λ					X		X				X	X	X	X
Assessments														
Adherence Self-Report		X			X					X	X	X	X	X
Self-Report Questionnaires §§		X					X					X		X
Usability and Satisfaction Survey					X							X*	X*	X*

\* Subjects randomized to intervention arm only

\*\* Three visits for witnessed doses; phase1: Week 1 and Week 2

§ Done per standard of care within 30 days of screening and captured whenever done during the course of the study

§§ Habitual self-control, self-efficacy beliefs, depression scale (PHQ-9), alcohol use (AUDIT) and drug use (DAST-10) questionnaires

λ Only subjects seen at UCSD AVRC will undergo collection of plasma for storage.

## 6.2 Evaluations

### 6.2.1 Pre-Entry Evaluations

Occur prior to the subject taking any study medications, treatments, or interventions.

#### 6.2.1.1 Patient Registration

A coded patient identification number (PID) will be assigned to each patient screened for the study. PIDs should not be reassigned even if the patient fails to enter the study. The PID must be included on every case report form (CRF) and patient blood sample. BIT Core must maintain a master list of PIDs in a central location. The patient registration and inclusion/exclusion CRF must be completed on the online system.

#### 6.2.1.2 Screening Clinical Labs

If plasma sputum, resistance testing, biochemistry, and hematology laboratories were obtained at a CLIA-approved lab no more than 90 days prior to screening and results are available then these labs do not need to be repeated. If these laboratories are not available from County records or medical records, then hematology, microbiology, chemistry, and pregnancy testing will be coordinated through the public health or AVRC laboratory and results will be tracked on the online database.

Screening entry evaluations in addition to screening laboratories will include documentation of TB, and medical and medication history with report of clinical assessment, including toxicity to TB treatment. Attitudes to mobile devices and internet usage, and ability to have a mobile device housed and charged at home will be ascertained. County healthcare workers will be asked about suitability of individual for inclusion in study. Once the screening laboratories and other evaluations have been done, the patient will be evaluated for study eligibility if all other entry criteria are satisfied.

If any laboratory values are outside the eligible range, the site may re-screen a patient on one occasion. However, the study will not pay for additional re-screening laboratories.

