### 3.3 Recruitment

The study will be advertised in flyers placed at PHS, OCHCA, San Ysidro Health Centers, and at UCSD. County outreach workers and healthcare personnel will inform all of their patients of this study, as will San Ysidro Health Centers and UCSD personnel involved in TB care. Interested patients will be directed to contact AVRC study personnel by phone. When patients interested in participating call, AVRC personnel will describe the study. They will inform patients that they may enroll in the study to undergo a two-week investigation of use and accuracy of DHFS IS-RM and then if willing and eligible, be randomized to the intervention with remote WOT via DHFS IS-RM, or to SOC DOT. The AVRC will establish the eligibility of potential participants (see above).

If a patient wants to participate, the study coordinator will then conference with the public health nurse and DOT outreach workers to review the patient's suitability for the study, including adequacy of living situation and ability to use mobile technology. If the patient is willing to participate and is recommended by PHS as able to participate, the patient will be scheduled for an appointment with AVRC personnel. At this appointment, AVRC personnel will again describe the study to the patient and confirm eligibility criteria (see above). Screening will include documentation of TB, smear negative or culture negative status, and resistance status as recorded, clinical assessment with targeted exam, concomitant medications and toxicities, and laboratory values obtained from CLIA certified clinical laboratories, within the last 30 days, or by County or AVRC laboratory if routine labs are unavailable (only lab values drawn by OCHCA staff will be used for Orange County participants), including complete blood count (CBC) with differential, chemistry panel and liver function tests (CMP), (abnormalities in these laboratory values will be reviewed by the PI or physician co-investigators prior to enrollment), and pregnancy test (as appropriate). The interviewer will assess the subject's attitude to mobile devices, understanding and experience of TB medications thus far, and whether they would be able to understand DHFS instructions of use and be willing to use all the components of the system. If the patient is viewed as able and eligible, the AVRC personnel will supervise signature of informed consent.

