## 4.0 SELECTION AND ENROLLMENT OF SUBJECTS

### 4.1 Inclusion Criteria

- 4.1.1 Basic competency in understanding written and verbal information as it applies to DHFS use.
- 4.1.2 Persons undergoing treatment for TB that includes at least isoniazid and rifampin at the time of entry to Phase 1; of note, patients must be sputum smear negative or culture negative at the time of study entry.
- 4.1.3 Laboratory values obtained by screening laboratories within 30 days of entry:
  - Absolute neutrophil count (ANC)  $\geq 1,000/\text{mm}^3$ .
  - Hemoglobin  $\geq 9.0$  g/dL.
  - Platelet count  $\geq 75,000/\text{mm}^3$ .
  - AST (SGOT), ALT (SGPT), and alkaline phosphatase  $\leq 3 \times \text{ULN}$ .
  - Total bilirubin  $\leq 1.5 \times \text{ULN}$  and direct bilirubin.
- 4.1.5 Females of childbearing potential must agree to use contraception throughout the study period.
- 4.1.6 Men and women age  $\geq 18$  years.
- 4.1.7 Eligible for anti-mycobacterial medications and in possession of prescriptions for isoniazid and rifampin, or Rifamate, as appropriate.
- 4.1.8 Willing to follow all protocol requirements.
- 4.1.9 Ability to use mobile device per investigator determination, and to wear PDH wearable sensor (i.e., no skin conditions precluding use).
- 4.1.10 Ability and willingness of subjects to give written informed consent.

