### 4.2 Exclusion Criteria

- 4.2.1 Female who is pregnant or breast-feeding, or of childbearing potential and has a tuberculin positive test at screening and disagrees to use contraception throughout the study period.
- 4.2.2 Use of any of the prohibited medications or other non-informed medications (Section 5.4.2) within 30 days of study entry.
- 4.2.3 Known hypersensitivity to any of the study drugs.
- 4.2.4 Known sensitivity to skin adhesives.

- 4.2.5 Serious illness requiring systemic treatment and/or hospitalization until subject either completes therapy or is clinically stable on therapy, in the opinion of the investigator, for at least 30 days prior to study entry (Day 0).
- 4.2.6 Evidence of any anti-mycobacterial resistance, clinical or genetic, prior to study entry. Resistance testing results must be available for review by the site investigator and study protocol team prior to enrollment to ensure that no exclusionary resistance exists.
- 4.2.7 Active drug or alcohol use, or dependence, or other conditions that, in the opinion of the site investigator, would interfere with adherence to study requirements.

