#### 6.2.1.3 Enrollment

Once a subject is deemed as eligible at screening they will be consented for enrollment into the study.

#### 6.2.1.4 Phase 1

The Day 0 evaluation should be scheduled within 45 days of the screening visit. Subjects will undergo training and instruction on the DHFS system and initiation of study drug with DOT. A clinical assessment including toxicity will take place on Day 0, Week 1, and Week 2. Subjects will be trained with the PDH system by study staff, including placing the patch under observation Day 0, Week 1, and Week 2. Subjects will begin DHFS IS-RM (or Rifamate with co-ingestion of an encapsulated edible sensor) on Day 0, which will be directly observed. Patients will have two study visits per week in Week 1 and Week 2 for directly observed ingestion of DHFS IS-RM (or Rifamate with co-ingestion of an encapsulated edible sensor). Monitoring for side effects will take place at visits. At the end of Week 2 the subject will have their plasma drawn and stored. All subjects will complete items on PDH system usability and satisfaction.

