## 7.2 Toxicity Management

Adverse events due to Tuberculosis or the medical treatment of TB (Rifamate) will be handled per SOC and County criteria. Laboratories to monitor toxicity will be done per County criteria and will be recorded by study forms.

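### Haematology and chemistry results up to 90 days old at screening may stand (6.2.1.2), although inclusion criterion 4.1.3 requires them within 30 days of entry

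*Combined protocol and SAP*

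**What the plan says.** Four parts of the protocol set an age limit for the eligibility bloods, and a fifth sets the gap between screening and Day 0.

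- **4.1.3 (Inclusion Criteria)** sets limits for neutrophils, haemoglobin, platelets, transaminases, alkaline phosphatase and bilirubin, under the lead-in "Laboratory values obtained by screening laboratories within 30 days of entry".
- **6.2.1.2 (Screening Clinical Labs)** covers sputum, resistance testing, biochemistry and haematology together. If these were obtained "no more than 90 days prior to screening and results are available then these labs do not need to be repeated". Testing is arranged where such results are not available.
- **3.3 (Recruitment)** lists, among the screening items, "laboratory values obtained from CLIA certified clinical laboratories, within the last 30 days".
- **Table 1 (6.1)** attaches this footnote to haematology, liver function and chemistry: "Done per standard of care within 30 days of screening". It adds that results are recorded whenever they happen to be done during the study.
- **6.2.1.4 (Phase 1)** gives the gap: "The Day 0 evaluation should be scheduled within 45 days of the screening visit". Table 1 shows the same 45-day window.

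**The concern.** The age limits differ in length (30 or 90 days) and in the date they count from (entry or screening). The protocol does not rank them. Its one precedence statement, in 9.6, concerns the SAP against that section.

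Site staff who work from 6.2.1.2 are told that a 60- or 80-day-old liver panel need not be repeated. Under 4.1.3 that panel cannot establish eligibility. Following one current section therefore produces a deviation from another. Site monitoring under 11.2.1 covers inclusion criteria for all patients, so such cases would be expected to surface as eligibility deviations.

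The second consequence is a stale liver and blood-count baseline for Phase 1. Table 1 marks haematology, liver function and chemistry at screening and next at Phase 2 Day 0. No draw is scheduled at Phase 1 Day 0 to close the gap, although a pregnancy test is repeated there.

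Sputum and resistance results are not part of this point. Criterion 4.1.3 sets no window for them, and a 90-day allowance for them conflicts with nothing in it.

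**Working it through.** **What entry means.** Exclusion 4.2.5 requires clinical stability "for at least 30 days prior to study entry (Day 0", placing Day 0 in brackets after study entry. Criterion 4.1.2 speaks of entry to Phase 1. The pregnancy-test paragraph in 6.3.9 calls for tests at screening and at study entry, and Table 1 marks them at screening and at Phase 1 Day 0. Together these identify entry as Phase 1 Day 0.

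**Inputs.**

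- Age allowed at entry: 30 days (4.1.3).
- Age allowed at screening: 90 days (6.2.1.2), or 30 days (3.3, where the screening anchor is implied, and the Table 1 footnote, where it is explicit).
- Gap allowed from screening to Phase 1 Day 0: 45 days (6.2.1.4 and Table 1).

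**Formula.** Oldest result at Day 0 = age allowed at screening + gap from screening to Day 0. Excess = that age − 30.

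| Situation | Age at Day 0 (days) | Excess over 4.1.3 (days) |
|---|---|---|
| 6.2.1.2, Day 0 with no delay after screening | 90 + 0 = 90 | 90 − 30 = 60 |
| Labs drawn on the screening day, Day 0 at the end of its window | 0 + 45 = 45 | 45 − 30 = 15 |
| 3.3 and Table 1, both windows at their limits | 30 + 45 = 75 | 75 − 30 = 45 |
| 6.2.1.2, both windows at their limits | 90 + 45 = 135 | 135 − 30 = 105 |

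The last two rows are worst cases. The first two need only one window at its limit.

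**If entry is read differently.** If entry in 4.1.3 meant screening, 3.3 and Table 1 would agree with it and their 15- and 45-day excesses would vanish. Section 6.2.1.2 would still allow 90 days against 30, an excess of 60.

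**After correction.** With 30 days counted back from Phase 1 Day 0, the oldest usable result is 30 days. If Day 0 falls 45 days after screening, the bloods must be drawn no earlier than 45 − 30 = 15 days after screening, so screening-day results would have to be repeated. A redraw is needed only when age at screening plus gap exceeds 30.

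The documents do not give the County's laboratory frequency before enrolment, so the proportion of subjects over 30 days cannot be calculated.

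**The case against.** The best reply is that the inclusion criterion governs anyway. Section 3.2 refers to the laboratory parameters in 4.1, 6.2.1.2 makes eligibility depend on the other entry criteria being met, and the inclusion/exclusion form has to be completed. Permission not to repeat a test is not a waiver of a criterion, so a careful site would query the conflict or redraw. This does point towards 4.1. It is not a precedence rule, however, and nothing described requires the date of the result to be checked at Day 0.

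Other points deserve weight:

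- Section 6.2.1.2 does have an age limit of its own, since results older than 90 days fall outside the allowance. The dispute is 90 against 30 days, not a missing limit.
- Sections 3.2 and 3.3 require physician review of abnormal values before enrolment. That review sees the values supplied; it is not described as testing their age.
- Under the Table 1 footnote, standard-of-care bloods taken between screening and Phase 2 Day 0 would be captured. That may close the gap for some subjects, but it guarantees no draw before Phase 1 Day 0.
- The word entry is used loosely. Section 6.2.1.5, for example, calls the dispensing day at randomization the entry day. This weakens the case against 3.3 and Table 1 somewhat, but not the case against 6.2.1.2. It is also a reason to name the anchor.

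The strongest part of the objection concerns consequence. Subjects already take isoniazid and rifampin at entry (4.1.2). Section 7.2 states: "Laboratories to monitor toxicity will be done per County criteria". Toxicity is assessed clinically at Phase 1 Day 0, Phase 1 lasts two weeks, and Table 1 marks bloods again at Phase 2 Day 0. All of that stands and limits the safety stake.

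**Conclusion.** The plan is wrong as written. Section 6.2.1.2 contradicts inclusion criterion 4.1.3 by 60 days before any delay to Day 0 is counted, and that part holds whether entry means screening or Phase 1 Day 0. The shortfall in 3.3 and Table 1, up to 45 days, rests on entry meaning Phase 1 Day 0, which 4.2.5 and the pregnancy-test schedule support. The 75- and 135-day figures are upper limits, not expected values.

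This should be corrected, but it is not a threat to the trial's conclusions. No primary endpoint uses these values, and sample size and the primary analyses are unaffected. What is at stake is avoidable eligibility deviations and a possibly outdated safety baseline for Phase 1, in an unknown number of subjects.

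**What to change.** 1. In 6.2.1.2, restrict the 90-day allowance to sputum and resistance results.
2. In 6.2.1.2, 3.3 and the Table 1 footnote, state that haematology and chemistry, including liver tests, must be dated within 30 days before Phase 1 Day 0, and be redrawn if Day 0 falls later than that.
3. Add a check to the existing form that Day 0 minus the laboratory date is 30 days or less. Section 6.2.1.1 already provides the place: "The patient registration and inclusion/exclusion CRF must be completed on the online system".

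The cost is wording in three sections, one date check, and an occasional repeat of a routine draw that 4.1.3 already requires. The revised text should also say who draws and pays for that repeat: 3.3 accepts only values drawn by Orange County agency staff for participants there, and 6.2.1.2 says the study does not fund additional re-screening bloods.
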